5.2.3 Deaths, Serious Adverse Events, and Other Significant Adverse Events

The following listings will be produced:

- A by-subject listing of all deaths that occurred during the study
- A by-subject listing of all serious adverse events
- A by-subject listing of all adverse events leading to discontinuation of study treatment
- A by-subject listing of all other adverse events of special interest

5.2.4 Clinical Laboratory Evaluation

For summaries by visit, the last non-missing assessment (including repeat assessments) recorded at each visit will be summarized. Unscheduled and unplanned assessments will be listed, but not included in by-visit summaries.

For across visit summaries (e.g., maximum post-baseline value), scheduled, unscheduled and repeat assessments will be considered.

A subject will be defined as having a treatment-emergent laboratory abnormality if the subject had a normal baseline value and an abnormal post-treatment start value.

The following summaries will be provided for each laboratory category:

- A summary of each laboratory parameters (absolute values and change from baseline) by treatment and visit
- A summary of the number and percentage of patients experiencing treatment emergent laboratory abnormalities by parameter, visit (and overall, throughout the study)
- A shift from baseline table by visit

Laboratory values for hematology, serum biochemistry, serological parameters and urine parameters will each be listed by subject and study time point including changes from baseline (with the exception of serological and urine parameters). The baseline for the laboratory values will be the last results obtained prior to treatment (Day 1 according to schedule)

All values outside the clinical reference ranges will be flagged in the data listings. The abnormal values will be flagged with 'L' for values below the lower limit of the clinical reference range and 'H' for values above the upper limit of the clinical reference range and included in the listings. The Investigator will assess whether the values outside the clinical reference range are clinically significant. Clinically significant laboratory values will be recorded by the Investigator as AEs.

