8.4. Adverse Events of Special Interest

The following AEs (SOC and PT) or laboratory findings of special interest will be evaluated by PIs at all study visits and time points (as applicable):

- Investigations (SOC):
 - Platelet count decreased (PT)
 - Neutrophil count decrease (PT)

Platelet and neutrophils count decrease with minor hematological impact (i.e., at a given study visit, a decrease in the platelet or neutrophil count less than a 30% from baseline's count) are not to be reported as an AE unless, in the opinion of the investigator, the decrease is clinically significant.

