1 INTRODUCTION

This document reveals the masked information in the blinded study protocol and may not be made available to Investigators and study-related staff in direct contact with the investigators (e.g., study monitors/CRAs) until general study unblinding.

The analyses described in this SAP are based upon the following study documents:

- Study Protocol, Version 5.0 (March 31, 2023)
- Clinical Study Protocol Addendum – Unmasked Information Version 4.0 (July 23, 2021)
- electronic Case Report Form (eCRF), Study Version 5.0 (June 7, 2022)

This SAP is written to be compliant with the ICH E7 guidelines.

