3.2 Endpoints

The study endpoints are listed below – all information presented in *italics* is masked in the blinded study protocol.

Primary endpoints – Efficacy

- To evaluate the difference on the Clinical Global Impression-Severity focused on Agitation/Aggression (CGI-S A/A) from baseline to *Weeks 8-12*, between the active treatment and the placebo arm.
- To evaluate the difference on the Borderline Personality Disorder Checklist (BPDCL), from baseline to *Weeks 8-12*, between the active treatment and the placebo arm

Secondary endpoints – Efficacy

- To evaluate the change overtime on the CGI-S A/A
- To evaluate the change over time on the BPDCL
- To evaluate the difference on the following measures, from baseline to *Weeks 8-12*, as well as change over time, between the active treatment arm and the placebo arm:
 - a) Borderline Evaluation of Severity over Time (BEST)
 - b) Beck Depression Inventory – II (BDI-II)
 - c) State-Trait Anger Expression Inventory 2 (STAXI-2)
 - d) State-Trait Anxiety Inventory (STAI)

Secondary endpoints – Safety

- To evaluate the following safety endpoints throughout the study, from baseline to week 14, including:
 - a) Number, frequency and severity of Treatment Emergent Adverse Events (TEAEs)
 - b) Number, frequency and severity of Serious TEAEs
 - c) Number and percentage of withdrawn subjects due to TEAEs
 - d) Frequency of physical examination parameters, vital signs and ECG parameters of potential clinical concern throughout the study period
 - e) Frequency of clinical laboratory parameters (hematology, including platelets, and clinical chemistry) of potential clinical concern throughout the study period
 - f) Columbia – Suicide Severity Rating Scale (C-SSRS)
 - g) Use of concomitant medication throughout the study period
- To evaluate the change from baseline to *Week 12* of the following safety endpoints:
 - a) Physical examination, vital signs and ECG parameters
 - b) Clinical laboratory parameters (hematology, including platelets, and clinical chemistry)

Exploratory endpoints

- To evaluate the difference on the following measures, from baseline to *Weeks 8-12*, as well as change over time, between the active treatment arm and the placebo arm:

- a) Columbia – Suicide Severity Rating Scale (C-SSRS)
 - b) Number of visits to healthcare services outside of the trial (primary care, mental health services and ER visits)
 - c) Agitation-Aggression Psychiatric Inventory-Clinician Report (AAPI-CR)

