4.2 General Statistical Considerations

'Baseline' is defined as the last available non-missing pre-treatment assessment. The average of screening and baseline values will be used as the baseline for effectiveness analysis. In the instance where only one value is present that value will be solely used as baseline. Change from baseline is calculated as visit value – baseline visit. 'End of Study' is defined as the last available post-treatment assessment. 'Treatment Day' will be calculated relative to the date of randomization (i.e., Treatment Day = Assessment Date - Randomization Date + 1). For safety summaries, the last pre-treatment measurement is defined as the baseline value.

When duration is calculated for an event (e.g., Adverse Events) and starting and ending date and time are both available, then, duration will be calculated as 'End datetime' – 'Start datetime' and presented in outputs in X day(s) hh:mm format. If time is missing or partially missing for either the end or the start of the event, then, duration will be calculated in days instead as 'End Date' – 'Start Date' + 1 Day.

Continuous data will be summarized in terms of the mean, standard deviation (SD), median, minimum, maximum, and number of observations, unless otherwise stated. The minimum and maximum will be reported to the same number of decimal places as the raw data recorded in the database. The mean, median, lower quartile and upper quartile will be reported to one more decimal place than the raw data recorded in the database. The SD will be reported to two more decimal places than the raw data recorded in the database. In general, the maximum number of decimal places reported shall be four for any summary statistic.

Categorical data will be summarized in terms of the number of subjects providing data at the relevant time point (n), frequency counts and percentages. Any planned collapsing of categories will be detailed in the SAP text and the data displays.

Percentages will be presented to one decimal place. Percentages will be calculated using 'n' as the denominator, unless otherwise stated.

Clinical rating scales may be summarized both as a continuous and as a qualitative variable, depending on the context.

Changes from baseline in categorical data will be summarized using shift tables where appropriate.

P-values greater than or equal to 0.001, in general, will be presented to three decimal places. P-values less than 0.001 will be presented as "<0.001".

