5.2.2 Adverse Events

Adverse events will be coded using the Medical Dictionary for Regulatory Activities (MedDRA) Version 23.1 or higher.

Treatment-emergent adverse events will be tabulated and are defined as those adverse events that either start or worsen in severity on or after the date/time of first dose of study treatment.

Where dates are missing or partially missing, adverse events will be assumed to be treatment-emergent, unless there is clear evidence (through comparison of partial dates) to suggest that the adverse event started prior to the first dose of study treatment.

For summary tables, AEs with “Certain”, “Probable/Likely” and “Possible” relationship to the study drug, as well as all AEs judged as unassessable/unclassifiable, will be considered related. In listings the more granular classification will be used.

The following AEs are considered to be of special interest:

- Investigations (SOC):
 - Platelet count decreased (PT)
 - Neutrophil count decrease (PT)

Only platelet and neutrophils count decrease with hematological impact (i.e., at a given study visit, a decrease in the platelet or neutrophil count *equal to or more than a 30% from baseline's count*) are to be reported as an AE unless, in the opinion of the investigator, the decrease is non-clinically significant.

An overall overview of TEAEs will be presented, including number of patients and frequency affected by different types of AEs as well as the number of events for each category by treatment:

- Any TEAEs
 - TEAEs related to study drug
 - TEAEs leading to study discontinuation
 - TEAEs by severity (mild, moderate severe)
 - TEAEs by outcome
- Any Serious TEAEs (STEAEs):
 - STEAEs related to study drug
 - STEAEs leading to study discontinuation
 - STEAEs by severity (mild, moderate severe)
 - STEAEs by outcome
- Any TEAEs of special interest
 - Platelet count decreased
 - Neutrophil count decreased
- Any COVID-19 TEAEs

The total number of subjects with at least one TEAE and the total number of TEAEs will be presented overall and by treatment arm and tabulated by MedDRA SOC and PT. In addition, AEs will be tabulated by worst severity and worst relationship to treatment.

The same tabulations will be provided for TEAEs, TEAEs of special interest, TEAEs leading to study drug discontinuation, serious TEAEs (STEAEs) and STEAEs related to study medication.

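### SAP 5.2.4 counts laboratory abnormalities only on a normal-to-abnormal change, so within-range platelet and neutrophil falls enter no laboratory patient count; a by-arm table of 30% and 50% falls would be a cheap, minor improvement

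*SAP*

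**What the plan says.** SAP 5.2.4 plans three laboratory summaries: absolute values and change from baseline by arm and visit; the number and percentage of patients with treatment-emergent abnormalities by parameter, by visit and overall; and a shift table by visit. The second counts a patient only "if the subject had a normal baseline value and an abnormal post-treatment start value". Size of change plays no part. Low and high flags are defined for the listings; the text does not say whether the incidence table separates them.

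The individual data are kept. Hematology values "will each be listed by subject and study time point including changes from baseline", and SAP 5.2.4 also provides: "For across visit summaries (e.g., maximum post-baseline value), scheduled, unscheduled and repeat assessments will be considered". By-visit summaries take the last non-missing result at the visit and leave out unscheduled tests. Their content is set in SAP 4.2: "Continuous data will be summarized in terms of the mean, standard deviation (SD), median, minimum, maximum, and number of observations". Protocol 9.3.6 grades the shift table in three levels: clinically significant abnormal, abnormal but not clinically significant, and normal.

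A secondary safety endpoint in SAP 3.2 is: "Frequency of clinical laboratory parameters (hematology, including platelets, and clinical chemistry) of potential clinical concern throughout the study period". Neither document gives it a criterion.

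Outside the laboratory tables, SAP 5.2.2 has a by-arm block headed "Any TEAEs of special interest", with separate lines for platelet and neutrophil decreases. There a fall of 30% or more is reportable unless the investigator considers it not clinically significant. Protocol 8.4 says that falls below 30% "are not to be reported as an AE unless, in the opinion of the investigator, the decrease is clinically significant".

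**The concern.** Protocol 5.2 names platelet and neutrophil depletion as the most relevant on-target tolerability effect. The program describes that effect by percent fall from baseline. A reduction over 50% set the animal no-effect level (Protocol 1.3), a platelet fall of 50% or more marked the intolerated human dose (1.4.1 and 5.2), and 1.2 mg/day was chosen as the highest dose with a platelet fall below 30% (1.6). The special-interest rule also uses 30%.

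The laboratory incidence table uses a different yardstick, reference-range status. A patient can lose a large share of the baseline count and remain normal by that standard. What is at stake is a plain description: how many patients per arm fell by 30% or by 50% at the dose under study. As planned, the first figure comes only through adverse-event reporting at about 20 sites, and the second is not produced.

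**Working it through.** The documents state no figure on this point, so there is none to reproduce. The check has two parts.

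**1. Does any planned display count patients by percent fall?**

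- Treatment-emergent incidence (SAP 5.2.4): counts patients, but only on leaving the reference range.
- Change from baseline by visit (SAP 5.2.4 with 4.2): includes every fall and shows the extremes, but counts nobody above a cut-off. A low first result followed by a recovered repeat at the same visit can also drop out, because the last result is used. SAP 4.2 has a general worst-case rule for safety data within a visit window, but 5.2.4 is the laboratory-specific text.
- Shift table (SAP 5.2.4, Protocol 9.3.6): counts patients by abnormality grade, not by percent fall.
- Listings: complete, but without counts.
- Special-interest events (SAP 5.2.2): patient counts by arm near 30%, filtered by the investigator; no 50% tier.

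**2. How large a fall can stay uncounted?**

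Let b be the baseline, L the laboratory's lower limit and f the fractional fall. The value stays in range if b(1 - f) >= L. The largest uncounted fall is therefore 1 - L/b, and a fall f stays in range from any baseline b >= L/(1 - f). The documents give no laboratory limits and no baseline distribution; L and b below are assumptions (x10^9/L).

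Largest uncounted fall, platelets:

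| Baseline | L = 130 | L = 140 | L = 150 |
|---|---|---|---|
| 200 | 1 - 130/200 = 35% | 30% | 25% |
| 250 | 1 - 130/250 = 48% | 44% | 40% |
| 300 | 1 - 130/300 = 57% | 53% | 50% |

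Largest uncounted fall, neutrophils:

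| Baseline | L = 1.5 | L = 1.8 | L = 2.0 |
|---|---|---|---|
| 3.0 | 1 - 1.5/3.0 = 50% | 40% | 33% |
| 4.0 | 1 - 1.5/4.0 = 63% | 55% | 50% |

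Baseline from which a fall stays in range:

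- Platelets, 30% fall: 130/0.7 = 185.7; 140/0.7 = 200.0; 150/0.7 = 214.3.
- Platelets, 50% fall: 130/0.5 = 260; 140/0.5 = 280; 150/0.5 = 300.
- Neutrophils, 30% fall: 1.5/0.7 = 2.14; 1.8/0.7 = 2.57; 2.0/0.7 = 2.86.
- Neutrophils, 50% fall: 3.0; 3.6; 4.0.

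Example: platelets going from 320 to 160 are a 50% fall, yet 160 lies above every assumed limit, so the incidence table does not count it.

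**Patients already low at baseline.** The definition also skips their further falls, but the group is small. Exclusion 8j bars platelets below 130,000/mm³ (130 x10^9/L) and neutrophils below 1,800/mm³ (1.8 x10^9/L), and Protocol 4.1 applies it at Screening and Baseline. For patients who meet those limits, the group is empty if L is at most 130 or 1.8. It is 130-149 for platelets if L = 150, and 1.8-1.99 for neutrophils if L = 2.0. SAP 5.1.1 does foresee some exclusionary blood values at the randomization visit.

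**The case against.** The strongest reply is that little is hidden, and most of it stands.

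- Within-range falls are not lost. They enter the change-from-baseline summaries, whose minimum shows the largest absolute fall per arm and visit, and they are listed. The gap is confined to patient counts.
- The shift table does count patients and can partly show worsening from an abnormal baseline. It still does not separate a 50% within-range fall from no change.
- The special-interest table already gives a by-arm count at about 30%, and filtering for clinical significance is a legitimate choice. However, it depends on site reporting. The SAP "may not be made available to Investigators and study-related staff in direct contact with the investigators", so sites work from Protocol 8.4, which implies, without stating it, that falls of 30% or more are reported.
- Some of the benchmarks can be read as dose-level or group-level findings. If the 30% in Protocol 1.6 is a group figure, the planned mean change by arm is the closer comparison. A reader might infer that the plan allows no comparison with the program's benchmarks; that goes too far.
- Protocol 5.2 reports no clinically relevant hematological impact at 0.6 or 1.2 mg/day in earlier Phase II trials, so few patients may cross either cut-off.

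A reader might also infer that the incidence table pools low and high values. The SAP is silent there, and the flags needed to separate them exist. Nor do the differing general rules in Protocol 7.3.5, 8.2 and 8.2.4 make the special-interest count void. Section 8.4 is the specific rule, and any conflict among the others is a separate matter that a laboratory table would not repair.

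**Conclusion.** The point holds as a minor, descriptive improvement. The laboratory incidence table leaves out within-range platelet and neutrophil falls. The only by-arm count near 30% is an investigator-filtered adverse-event count, and no 50% count is planned. That follows from the text. The illustrated sizes rest on assumed reference limits and baselines.

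A reader might go further and conclude that the trial will materially under-report hematological toxicity or that patients are less safe. The documents do not support either conclusion. They give no reference range, baseline distribution or rate of such falls at 1.2 mg from which an under-count could be estimated, and Protocol 1.6 and 5.2 suggest that it may be small. Platelets are checked at every visit, and study drug is halted if a check is missed (Protocol 7.3.5). It also cannot be said that the monitoring committee would miss these falls: the regular displays include adverse-event summaries and listings, and SAP 5.2.11 leaves the details to a separate shell document. No test, primary endpoint or stopping rule changes.

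**What to change.** In SAP 5.2.4, for platelets and neutrophils:

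1. Add a table by arm, in the SAF, of patients with a baseline and at least one value after first dose. Give n (%) whose lowest value after first dose, up to and including Visit 8/EoS, is at least 30% and at least 50% below baseline, whatever the baseline category. Use scheduled, unscheduled and repeat tests, as the across-visit rule already allows.
2. Show Visit 9 separately, because all participants take placebo between Visits 8 and 9 (Protocol 5.1.1).
3. Tabulate treatment-emergent abnormalities as new low and new high, using the flags already defined.
4. Place the counts beside the special-interest table. Do not declare 30% or 50% to be the definition of potential clinical concern: that would class values well inside the range as concerning without clinical judgement, and would leave the endpoint undefined for every other parameter.

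The cost is SAP wording and one extra table from central-laboratory data already collected, with no new visits or samples. The drawback is that some falls of no clinical significance will be counted.

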5.2.5 Vital Signs

Vital signs results will be listed by patient and visit, including changes from baseline and assessments as abnormal/normal, and if abnormal, as clinically significant or not clinically significant.

Descriptive statistics will be provided for each vital sign parameter by visit/time point and treatment, including changes from baseline.

5.2.6 Physical Examinations

The results of the physical examination will be listed by subject.

5.2.7 Pregnancy Tests

The results of the pregnancy tests will be listed by subject.

5.2.8 Urine Drug Screen Results

The results of the urine drug screen will be listed by subject.

5.2.9 Electrocardiograms

ECG parameters will be listed by patient and visit, including changes from baseline and overall assessment as abnormal/normal, and if abnormal, as clinically significant or not clinically significant.

Descriptive statistics will be provided for each parameter by visit/time point and treatment, including changes from baseline. Categorical summaries of ECG findings will be presented in an additional table.

5.2.10 Columbia-Suicide Severity Rating Scale

The C-SSRS results will be listed.

The following items will be summarized by treatment and visit:

- Number and percentage of patients who answered at least one of the questions 1 and 2 with “yes” under Suicidal Ideation
- Number and percentage of patients answering each of the questions 1 to 5 with “yes”
- For the patients who answered “yes” to questions 1 and 2:
 - Number and percentage in each category (1 to 5) for most severe suicide ideation
 - Answers (number and percentages per answer) to the Intensity of Ideation questions
- Number and percentages for the answers to the questions under Suicidal Behavior
- Number of actual suicide attempts

The same table – especially the number and frequency of patients who committed actual suicide attempts since the last visit – is used for the evaluation of C-SSRS as an exploratory efficacy endpoint.

Responses to each item will be listed by patient.

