State-Trait Anger Expression Inventory 2 (STAXI-2)		X	X	X	X	X	X	X	X	X ⁽⁵⁾
Clinical Global Impression-Severity for Agitation/Aggression (CGI-S A/A)		X	X	X	X	X	X	X	X	X ⁽⁵⁾
Number of visits to healthcare services outside of the trial (primary care, mental health services & ER visits)			X ⁽⁷⁾		X ⁽⁷⁾		X ⁽⁷⁾		X ⁽⁷⁾	X ⁽⁵⁾
Safety Assessments										
Adverse events			X	X	X	X	X	X	X	X
Vital signs ⁽⁸⁾		X	X	X	X	X	X	X	X	X
Electrocardiogram ⁽⁸⁾		X							X	
Blood sample for laboratory safety assessments ⁽⁸⁾										
Hematology		X	X	X	X	X	X	X	X	X ⁽⁵⁾
Biochemistry		X	X	X	X	X	X	X	X	X ⁽⁵⁾
Hep C, Hep B, HIV testing		X								
Blood sample for pharmacokinetic and target engagement ⁽⁹⁾										
PK ⁽⁹ⁱ⁾			X		X ⁽⁹ⁱ⁾		X ⁽⁹ⁱ⁾		X	
LSD1-TE			X		X		X		X	
Blood sample for exploratory assessments ⁽¹⁰⁾										
Biomarkers' analysis			X						X	
Genotyping			X							
Investigational Medicinal product (IMP)										
Assess IMP compliance (manual accountability of returned IMP at site)				X	X	X	X	X	X	X ⁽⁵⁾
Dispense IMP ⁽¹¹⁾			X	X	X	X	X	X	X ⁽⁵⁾	

[figure not shown]
* Screening period can last up to two-weeks with a window of ± 7 days.

(1) All assessments from a specific visit may be completed over a maximum of two consecutive days. In this case, the first day should be considered as the visit day. The forecasting for visit schedule should take V2 (Baseline) date as the reference. If the date of a visit changes within the allowed window, the following visits will still be scheduled based on V2 (Baseline) date.

(2) After Visit 2, seven visits, every two weeks, are planned until Visit 9. If participants do not complete all study visits (early termination), then they should complete all the Visit 8/EoS assessments. All participants are classified as follows:

- a. *Completers*: Participants completing Visit 9.
 - b. *Non-completers*: Participants that received at least one dose of study treatment, but prematurely discontinued the study before completion of Visit 9 for any reason other than withdrawal of the informed consent. These participants will be asked to complete an End of Study (EoS) Visit as soon as possible after withdrawal. Non-completers will not enter the 2-week participant-blind placebo run-out period.
 - i. If there has been, at least, one week between the last intake of study drug and this EoS visit, no further Safety follow-up visit will be required.

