- j) The concomitant use of nootropics; for instance, racetams, amphetamines, methylphenidate, levodopa, atomoxetine, preparations containing Ginkgo biloba in stable dose for at least 2 months before Screening are allowed for the treatment of psychiatric comorbidities (as per inclusion/exclusion criteria) when these medications are prescribed as per their labelled indications.
- k) The concomitant use of centrally active anti-hypertensive drugs, such as clonidine, α-methyldopa, and guanfacine, as well as guanethidine, in stable dose for at least 2 months before Screening are allowed but should be used with caution.
- l) The concomitant use of medications which may have an impact on blood count changes should be used with caution (e.g.: heparin, quinine, quinidine, penicillin, sulfonamides, NSAIDs, anticonvulsants, antirheumatics, oral antidiabetics, gold salts, diuretics rifampicin, ranitidine). This list is not intended to be exhaustive. Drug-Drug Interactions (DDI) interactions should be reviewed in the label of the concomitant medication.
- m) The concomitant use of platelet aggregation inhibitors should be used with caution (e.g.: COX-2 inhibitors, ADP receptor inhibitors, thromboxane inhibitors). This list is not intended to be exhaustive. Drug-Drug Interactions (DDI) interactions should be reviewed in the label of the concomitant medication.

13. Esketamine in the past 90 days before the Screening visit.

14. Electroconvulsive therapy (ECT) or transcranial magnetic stimulation (TMS) in the past 90 days before the screening visit.

15. Any regular intake of medications acting directly on central nervous system that investigator considers relevant to the study.

16. Member or immediate family of the study personnel or subordinate to any of the study personnel.
17. Enrollment in another investigational study or intake of investigational drug within the previous 3 months.
18. Suicide attempt within the 6-month prior to the Screening visit or significant risk of suicide (in the opinion of the investigator, defined as a “yes” to suicidal ideation questions 4 or 5, or answering “yes” to suicidal behavior on the Columbia-Suicide Severity Rating Scale within the past 6-months).
19. Any condition that in the opinion of the investigator makes the participant unsuitable for inclusion in the study.

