4.2. Removal of Participants from Therapy or Assessment

Participants are free to discontinue trial participation at any time. Withdrawal from the trial will not affect or prejudice participants further care or treatment. In addition, participants may be withdrawn from study treatment and assessments at any time, if deemed necessary by the PI or Sponsor.

Potential reasons for withdrawal of participants from this study include, but are not limited to:

- The participant withdraws his or her consent (defined as a participant who explicitly takes back his or her consent)
- The PI considers it, for safety and/or study compliance reasons, in the best interests of the participant that he or she be withdrawn
- Initiation of concomitant medication prohibited by the study protocol (see [Table 2](#))
- Initiation of psychotherapy in psychotherapy naïve participants at baseline
- Discontinuation of psychotherapy in participants receiving therapy at baseline
- Pregnancy
- Participant is lost to follow-up (defined as a participant who fails to comply with scheduled study visits or contact, who has not actively decided to withdraw from the study, and for whom no alternative contact information is available [this implies that at least two attempts have been made to contact the participant])
- Any center personnel break the randomization code for that participant
- The participant attempts suicide or is at significant risk of suicide (either in the opinion of the investigator or defined as a “yes” to suicidal ideation questions 4 or 5 or answering “yes” to suicidal behavior on the C-SSRS during the study)

The reason and date the participant is withdrawn from the study and further treatment with the IMP will be documented in the electronic case report form (eCRF) (e.g., lost to follow-up, consent withdrawn, incorrect enrollment, AEs, etc.).

If a participant is withdrawn from the study, the PI should attempt to complete all study assessments in [Table 1](#) for the EoS Visit.

Participants who withdraw due to an AE should be followed until resolution of the AE, or the PI or delegated center personnel decides that the AE is stable, and the participant does not need further follow-up. All AEs should be followed up according to Section 8 [ADVERSE EVENTS](#).

If a participant is withdrawn from the study, all data collected until the time of withdrawal will be included in the analyses.

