Listings of participants with STEAEs, deaths and STEAEs leading to discontinuation and individual narratives for these cases will be provided.

Physical Examinations

Physical examination results including assessment as “normal” or “abnormal” and clinical significance of abnormalities will be listed. New abnormalities do not present at baseline will be flagged.

Vital Signs

All abnormal vital signs including assessment of clinical significance will be listed by participant. Summary statistics for vital sign parameters will be provided (absolute and change from baseline) by actual treatment arm and visit.

Electrocardiograms

All abnormal ECG results will be listed by participant including assessment of clinical significance and description of any abnormality. ECG parameters (absolute values and changes from baseline) will be summarized by actual treatment arm and visit.

Columbia-Suicide Severity Rating Scale

The C-SSRS results will be listed and summarized descriptively by actual treatment arm and visit.

Laboratory Safety Assessments

All abnormal laboratories including assessment of clinical significance will be listed by participant. Laboratory parameters (absolute values and changes from baseline) will be summarized by actual treatment arm and visit.

Shift tables will be produced for post-baseline time points and overall results per each parameter. Results will be defined as clinically significant abnormal > clinically non-significant abnormal > normal.

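### C-SSRS, a study-long safety endpoint, is summarised only by arm and visit; no participant-level on-treatment incidence and no comparison with baseline is specified

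*SAP*

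**What the plan says.** SAP 3.2 places C-SSRS in a list of secondary safety endpoints introduced by "To evaluate the following safety endpoints throughout the study, from baseline to week 14, including". The stated period is therefore the study as a whole.

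The planned summaries are by visit. SAP 5.2.10 introduces its list of ideation, intensity, behaviour and attempt summaries with "The following items will be summarized by treatment and visit". Protocol 9.3.6 matches: "The C-SSRS results will be listed and summarized descriptively by actual treatment arm and visit". The SAP also uses this one table as the exploratory efficacy output and singles out "the number and frequency of patients who committed actual suicide attempts since the last visit", which is a count per interval between visits. Individual responses are listed.

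Two protocol rules bear on who can be positive and who remains. Exclusion criterion 18 (Protocol 4.1.2) covers "Suicide attempt within the 6-month prior to the Screening visit or significant risk of suicide", where risk means ideation item 4 or 5 or suicidal behaviour within six months. Protocol 4.2 gives "The participant attempts suicide or is at significant risk of suicide" as one entry in a list headed "Potential reasons for withdrawal of participants from this study include, but are not limited to". Withdrawal is thus possible but not mandatory.

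**The concern.** For a safety endpoint defined over the whole study, the natural question is how many participants in each arm had serious ideation, suicidal behaviour or an attempt while on treatment, and how many became worse than they were before dosing. The C-SSRS summaries as written answer neither.

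Exclusion 18 makes the question sharper. Because participants with these answers in the previous six months are kept out, such answers on study are mostly new relative to that window, though not relative to lifetime history. An incidence per arm is the summary that suits this.

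The SAP treats other safety data differently. For laboratory data, 5.2.4 provides across-visit summaries, such as the maximum post-baseline value, and a count of participants with abnormalities over the whole study. For adverse events, 5.2.2 counts participants with at least one event. Section 5.2.10 has no counterpart to either. Among the displays that SAP 5.2.11 names for regular DMC meetings, C-SSRS appears only as a listing.

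**Working it through.** **Number of visits.** Table 1 of the protocol states "After Visit 2, seven visits, every two weeks, are planned until Visit 9". Weeks 2, 4, 6, 8, 10, 12 and 14 give 7 post-baseline visits (V3 to V9), with C-SSRS scheduled at each. Protocol 5.1.1 gives placebo to everyone from V8 to V9, so 7 − 1 = 6 visits (V3 to V8) fall on randomised treatment. The plan's figure of seven is reproduced; an on-treatment summary rests on six.

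**Denominator.** SAP 4.2 bases percentages on the participants providing data at the time point, so a withdrawn participant leaves the denominator of later visits. The same section maps early-termination and unscheduled assessments to the closest scheduled visit and takes the worst case for safety data, so an assessed case is kept at the visit where it occurs.

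**What visit counts reveal about participants.** Let c1 to c6 be the numbers positive at the six on-treatment visits in one arm. The number of participants ever positive, P, satisfies

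max(c1,…,c6) ≤ P ≤ c1 + … + c6.

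The lower bound is reached if the same people are positive each time, which requires that they stay. The upper bound is reached if nobody is positive twice.

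The documents give no suicidality rate, so the visit counts below are assumptions. The arm size is 188/2 = 94 (SAP 3.1), and dropout is ignored for simplicity.

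| Assumed positives per visit | Lowest P | Highest P (6 × count) | Range of incidence |
|---|---|---|---|
| 1 | 1 | 6 | 1/94 = 1.1% to 6/94 = 6.4% |
| 2 | 2 | 12 | 2/94 = 2.1% to 12/94 = 12.8% |
| 4 | 4 | 24 | 4/94 = 4.3% to 24/94 = 25.5% |

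Two arms could show identical visit rows, two positives at every visit, with incidences up to 10/94 = 10.6 percentage points apart. These are logical extremes and not a forecast. They show that the planned table does not determine the incidence.

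**Change from baseline.** None of the items in SAP 5.2.10 relates a post-dose category to the participant's own pre-dose category. SAP 4.2 allows shift tables where suitable, but 5.2.10 does not call for one.

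**The case against.** The strongest reply is that suicidality is already counted once per participant. The TEAE and serious-TEAE tables (SAP 5.2.2) count participants with at least one event by arm, system organ class and preferred term, and the disposition table (SAP 4.4.1) gives discontinuations with their primary reason. This stands for any attempt or ideation recorded as an adverse event, so it would be wrong to say that suicidality is nowhere summarised per participant. It does not close the gap. The documents do not require a positive C-SSRS answer to be recorded as an AE, and the only events of special interest are platelet and neutrophil decreases. Disposition misses cases who stay.

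A second reply is that the listing lets anyone count later. That is so, but the window, the reference category and the handling of unscheduled visits would then be chosen after unblinding.

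Some stronger readings are tempting and are not supported:

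- **Late-visit percentages favour the arm that loses more cases.** This needs higher-risk participants to be depleted. Assume instead a constant risk per visit, 14% of 94 affected over seven visits, and every case withdrawn. The risk per visit is 1 − 0.86^(1/7) = 2.13%, and the expected rows are 2.00, 1.96, 1.92, 1.88, 1.84, 1.80 and 1.76. The last percentage is 1.76/(94 − 11.40) = 2.13%, equal to the first, 2.00/94.
- **Visit counts can never be added.** In that same case the rows sum to 13.16 = 14% of 94. Addition fails when participants stay and are positive again.
- **The display costs statistical power.** No test of C-SSRS is planned, and any power figure would rest on rates that the documents do not give.
- **The protocol's 10% suicide figure is the expected background here.** Protocol 1.1 describes completed suicide, which may come years after first presentation. It is not a 14-week rate, and exclusion 18 removes recent high-risk cases.

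**Conclusion.** The concern holds as a gap in the planned summaries. C-SSRS is specified only by treatment and visit, in a single table, and that table does not in general yield the number of participants affected on treatment or the number who worsened from their own baseline. The AE tables cover only part of this.

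The illustration (for example 2.1% to 12.8% from the same visit rows) rests on assumed visit counts, 94 per arm and no dropout. How far the true incidence would be obscured depends on how often participants are positive more than once and how many are withdrawn, and the documents give neither. The point does not touch the primary analysis or any clinical rule. It should be corrected because it limits what the trial can report on a stated safety endpoint and the data are already collected.

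**What to change.** This is an analysis change only; no withdrawal or other clinical rule is affected.

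Add to SAP 5.2.10, on the SAF by actual arm, the number and percentage of participants with at least one of each of the following between first dose and V8/EoS:

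- (a) ideation item 4 or 5;
- (b) suicidal behaviour;
- (c) an actual attempt;
- (d) an ideation category worse than the worst pre-dose category.

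Count each participant once per row, using scheduled, early-termination and unscheduled assessments. Show the V8 to V9 placebo run-out separately. Add a shift table from worst pre-dose to worst on-treatment category, and a descriptive risk difference with 95% CI for (a) or (b). Give the DMC the same table beside the listing. Keep the by-visit table.

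The definition should also state on which side of first dose the Visit 2 C-SSRS falls, since Protocol 5.1.6 puts the first capsule before the rating scales at that visit.

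The cost is programming one table and one shift table from data already collected. Protocol 9.5 allows the SAP to be amended before unblinding; a change after database lock belongs in an SAP addendum or the study report, with its justification.
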